## 1.0 Background

There is limited safety information on Adcetris IV Infusion 50 mg (hereinafter referred to as Adcetris) collected from Japanese patients in Japanese phase 1/2 studies. It is important to promptly collect post-marketing safety information and provide it to healthcare providers. It was also deemed that additional surveillance was required to determine the occurrence of peripheral nerve disorders, infections, neutropenia, infusion reactions, and pulmonary disorders in patients using Adcetris in Japan as post-marketing safety specifications.

Thus, an all-case surveillance in all patients receiving treatment with Adcetris will be initiated as an additional pharmacovigilance activity for Adcetris when the drug is launched.

This surveillance study will be conducted in compliance with the GPSP Ordinance and other related regulatory requirements.

## 2.0 Purpose

The purpose of this study is to evaluate the safety of Adcetris in patients with relapsed/refractory CD30+ Hodgkin's lymphoma or anaplastic large cell lymphoma in the routine clinical setting, as well as to collect efficacy information for reference.

## 3.0 Estimated Enrollment and Its Rationale

### 3.1 Estimated enrollment

140 patients (with relapsed/refractory CD30+ Hodgkin's lymphoma or anaplastic large cell lymphoma)

### 3.2 Rationale

It is expected that the detailed evaluation of peripheral nerve disorders, infections, neutropenia, infusion reactions, and pulmonary disorders will help better understand the safety profile of Adcetris in the routine clinical setting, which will lead to the assessment of the risk-benefit balance of the drug.

The frequencies of peripheral nerve disorders, infections, neutropenia ( $\geq$ Grade 3), infusion reaction, and pulmonary disorder in non-Japanese phase 2 studies (pooled study data from a study in patients with Hodgkin's lymphoma [SG035-0003, 102 patients] and a study in patients with systemic anaplastic large cell lymphoma [SG035-0004, 58 patients]) were 56%, 61%, 20%, 11%, and 6%, respectively.

Observation of infusion reactions with the lowest frequency of  $\geq 10$  patients, aside from pulmonary disorders, with a probability of 95% would require 140 patients, which was therefore determined to be the estimated enrollment. It is estimated that when the number of patients enrolled reaches 140 patients,  $\geq 4$  patients have adverse events of pulmonary disorder with a probability of 95%.

## 4.0 Eligible Patients

All patients receiving treatment with Adcetris

## 5.0 Dosage Regimen

The usual adult dosage is 1.8 mg/kg (body weight) of brentuximab vedotin (recombinant) infused intravenously once every three weeks. The dose should be adjusted depending on the patient's condition.

See the "PRECAUTIONS" section of the package insert.

## 6.0 Expected Study Institutions by Department

The study will be conducted at all institutions using Adcetris (e.g., department of hematology) (approximately 100 study institutions are expected to participate in the study).

## 7.0 Methods

### 7.1 Observation period

From the start of treatment with Adcetris until the completion of 16 cycles [3 weeks per cycle]

#### \* Rationale for the selection of the observation period

The assessment of the treatment cycle with the initial onset of adverse events in a clinical study [SGN35-006, the extended treatment group] evaluating the safety of Adcetris after Cycle 17 showed a tendency that most adverse events occurred before Cycle 16. In addition, the types and severities did not differ between adverse events occurring after Cycle 17 and those occurring before Cycle 16. This suggested that the safety profile of Adcetris would be generally determined before Cycle 16. Therefore, the observation period was defined as the period from the start of treatment with Adcetris until the completion of 16 cycles.

### 7.2 Request for participation in this study and contract with each study institution

Paper-based case report forms will be used. To ask each study institution to participate in the study, the representative of Takeda Pharmaceutical Company Limited (representative of Takeda) will confirm before supply of Adcetris and the start of the study that each study institution meets all requirements for study institutions and investigators specified below, and have a written contract with the study institution after prior explanation of the study provided before supply of Adcetris.

#### (1) Requirements for each study institution and investigator

##### 1) Requirements for each study institution

[1] Is able to cooperate with this all-case surveillance and have a contract with the sponsor.

[2] Is able to provide specialized treatment for hematopoietic tumors.

[3] Is able to provide emergency treatment if required (including a case where such a treatment can be provided in conjunction with another institution

).

\* When emergency treatment is provided in conjunction with another institution, information on Adcetris safety measures and treatment of adverse drug reactions should be shared between the institution and the other institution to build a coalition.

2) Requirements for each investigator

[1] Has adequate knowledge and experience regarding the treatment of hematopoietic tumors, or is under the direction of a healthcare professional having such knowledge and experience.

[2] Is able to cooperate with this all-case surveillance.

(2) Prior explanation of the study to be provided before supply of Adcetris and the request for participation in this study

Using “Request for Participation in the Special Drug Use Surveillance,” “Study Outline,” “Patient Enrollment Form (sample),” “Case Report Form Parts 1 and 2 (sample),” “Precautions for Use/Instruction Manual,” and “Proper Usage Guide,” the representative of Takeda will explain the purpose and methods (e.g., all-case surveillance) of this survey study and information regarding the proper use of Adcetris to the investigator and ask him/her to participate in the all-case surveillance.

The representative of Takeda will also confirm with the investigator that the institution and the investigator meet all requirements.

(3) Request for participation in this study and contract with each study institution

The representative of Takeda will have a written contract with the study institution after obtaining their agreement to participate in this study. Takeda Pharmaceutical Company Limited will inform the outsourced Adcetris supplier that the contract is concluded and Adcetris should be supplied to the study institution. The representative of Takeda will deliver patient enrollment forms to the investigator.

7.3 Method of patient enrollment

The central enrollment method via FAX will be used. For each patient scheduled to receive treatment with Adcetris after the date of the start of the term of the contract with the study institution, the investigator will complete patient enrollment by submitting the Patient Enrollment Form with information required for patient enrollment filled in (see Section 9.1) via FAX to the Central Enrollment Center (see Section 12.3) until noon of the day before the date of the expected initial dose of Adcetris.

The Central Enrollment Center will review the Patient Enrollment Form and send the Enrollment Completion Notice to the investigator via FAX. After receiving the Enrollment Completion Notice, the investigator will initiate treatment with Adcetris.

The Case Report Form consists of Parts 1 and 2 per patient.

The representative of Takeda will deliver Case Report Form Part 1, which is issued after enrollment confirmation by the Central Enrollment Center, to the investigator. Case Report Form Part 2 is issued after Takeda Pharmaceutical receives Case Report Form Part 1.

#### 7.4 Completion and submission of the case report form

For all patients requiring the completion of the case report form, the investigator will complete the case report form during the period from the start of treatment with Adcetris until the end of Cycle 4 and within 1 month after the end of Cycle 16, and submit it to the representative of Takeda.

If treatment with Adcetris is discontinued for any reason before the end of the observation period, the investigator will complete the case report form within 1 month after the completion of required observation submit it to the representative of Takeda. If treatment with Adcetris is discontinued due to any adverse event, however, the investigator will continue to observe the patient after treatment discontinuation until the adverse event resolves or improves wherever possible, and then complete the case report form and submit it to the representative of Takeda.

#### 7.5 Confirmation of all-case surveillance

After the completion of the study, the principal investigator will confirm that case report forms of all patients treated with Adcetris have been submitted, and sign or fill in his/her name with seal on All-Case Surveillance Confirmation Form and submit it to the representative of Takeda.

#### 8.0 Estimated Study Period

Study period: Starts on the day of the launch of Adcetris (April, 2014) and ends once the all-case surveillance is no longer a condition for approval of the product.

Patient enrollment period: Starts on the day of the launch of Adcetris (April, 2014) and ends once the all-case surveillance is no longer a condition for approval of the product.

The expected number of enrolled patients (140) was achieved. Therefore, the study will move to the period only requiring patient enrollment (not requiring the completion and submission of case report forms).

After moving to the period only requiring patient enrollment, it may be required to complete and submit case report forms upon request by the regulatory authority.

#### 9.0 Outcome Measures

The investigator will record data listed below in both Patient Enrollment and Case Report Forms. Study schedule is provided in in Appendix 1.

## 9.1 Data to be recorded in Patient Enrollment Form

### 1) Outcome measures

Name of the institution, name of the investigator completing Patient Enrollment Form, expected date of the start of treatment with Adcetris, patient identification number, patient initial, sex, date of birth, diagnosis, performance status, CD30, past history of severe hypersensitivity to any ingredient of Adcetris, expected concomitant use of other antineoplastic drugs, and presence/absence of infections, peripheral nerve disorders, hepatic disorders, severe renal disorders, or pregnancy/breast-feeding

### 2) When to collect outcome measure data

At the time of patient enrollment

## 9.2 Data to be recorded in Case Report Form

### 9.2.1 Cover sheet of Case Report Form

Date of the final completion of Case Report Form and name of the investigator completing Case Report Form

### 9.2.2 Patient demographics and baseline characteristics

#### 1) Outcome measures

Date of diagnosis of Hodgkin's or anaplastic large cell lymphoma, site of involvement, ALK (in patients with anaplastic large cell lymphoma), clinical stage, presence/absence of B symptoms, ECOG Performance Status, therapeutic category, (presence/absence and detail of) hypersensitivity disposition, viral test results, past history of and concurrent pulmonary disorders, past history of and concurrent malignant tumours, (presence/absence and detail of) concurrent illnesses [other than pulmonary disorders and malignant tumours], (presence/absence and detail of) past history [other than pulmonary disorders and malignant tumours], height, weight, smoking history, and (presence/absence and detail of) prior treatment for Hodgkin's lymphoma or anaplastic large cell lymphoma (including drug therapy, radiotherapy, and hematopoietic stem cell transplantation)

#### 2) When to collect outcome measure data

At the start of treatment with Adcetris

### 9.2.3 Treatment given

#### 1) Outcome measures

Treatment with Adcetris and premedication to prevent infusion reaction (dose, date of premedication, and reasons for premedication to prevent infusion reaction and its discontinuation), (use or non-use, type, and date of) post-baseline hematopoietic stem cell transplantation, (presence/absence, name, and duration of) drugs other than Adcetris used for the treatment of the primary disease, and (presence/absence, name, and duration of) drugs used for the prevention of infection

#### 2) When to collect outcome measure data

From the start of treatment with Adcetris until the completion of 16 cycles (or upon discontinuation of treatment with Adcetris)

#### 9.2.4 Tests and assessments

##### 9.2.4.1 Laboratory tests

###### 1) Outcome measures

Red blood cell count, hemoglobin level, white blood cell count, neutrophil count, lymphocyte count, platelet count, total bilirubin, AST, ALT, LDH, BUN, and serum creatinine

###### 2) When to collect outcome measure data

At each test time point during the period from the start of treatment with Adcetris until the completion of 16 cycles (or upon discontinuation of treatment with Adcetris)

##### 9.2.4.2 Best response

###### 1) Outcome measures

The best response (CR, CRu [for patients with no PET scan data], PR, SD, or PD) will be assessed based on CT and PET scans of the neck, chest, abdomen, and pelvis according to the best response assessment criteria (see Appendix).

###### 2) When to collect outcome measure data

After 16 cycles of treatment with Adcetris (or upon discontinuation of treatment with Adcetris)

##### 9.2.4.3 Date of the final observation

###### 1) Outcome measures

Date of the final observation

###### 2) When to collect outcome measure data

After 16 cycles of treatment with Adcetris (or upon discontinuation of treatment with Adcetris)

##### 9.2.4.4 Other assessments

###### 1) Outcome measures

Pregnancy during the observation period (for females only)

If pregnancy is detected during the observation period, it should be reported to the representative of Takeda immediately.

###### 2) When to collect outcome measure data

From the start of treatment with Adcetris until the completion of 16 cycles (or upon discontinuation of treatment with Adcetris)

#### 9.2.5 Adverse events

##### 1) Outcome measures

Presence/absence of adverse events (see Table 1), adverse event terms, date of onset, CTCAE grade (the worst one), seriousness and its reason (see Table 2), (presence/absence and detail of) action taken to Adcetris, (presence/absence and detail of) intervention for adverse events, date of outcome, outcome, causal relationship with Adcetris\* (see Table 3), and changes in laboratory test values associated with adverse events over time

If the outcome is “not recovered/not resolved” or “unknown,” and the causal relationship with Adcetris is considered unevaluable, the event should be followed wherever possible.

\* If the event is considered not related to Adcetris, its rationale should be collected. If the causal relationship with Adcetris is considered unevaluable, its reason should be collected.

Note) Points to consider regarding adverse events

Worsening of the primary disease should not be regarded as an adverse event. However, abnormal worsening of the primary disease (e.g., worsening beyond the expected natural course of the disease) should be regarded as an adverse event.

Disease progression should be regarded as worsening of the primary disease rather than an adverse event. However, clinical or laboratory progression of an existing cancer (including new metastasis) that meets any of the criteria for the seriousness of adverse events (see Table 2) should be considered a serious adverse event.

## 2) Adverse events of particular interest

The events listed below are events of particular interest; detailed information on these events should be collected wherever possible if they are observed:

- Peripheral nerve disorders
- Infections
- Neutropenia
- Infusion reactions
- Pulmonary disorders

\* Rationale for the selection of adverse events of particular interest

Of important identified risks listed in Risk Management Plan, those listed above were selected as adverse events of particular interest based on the following rationales:

### a) Peripheral nerve disorders

Peripheral nerve disorders are frequently observed after treatment with Adcetris. If the event of peripheral nerve disorder becomes severe, it is difficult to continue treatment with Adcetris. It is important to control the onset of the event to allow for continuation of treatment (including dose reduction and restart of treatment after treatment interruption). Therefore, the profile of peripheral nerve disorders in Japanese patients as an adverse event of particular interest will be determined (i.e., information useful for continuation of treatment with Adcetris, including risk factors, commonly reported time to onset, outcomes, and the status of treatment with Adcetris, will be collected).

### b) Infections

It is expected that Adcetris is used in patients who are immunocompromised due to prior treatment or the prior disease or those who are complicated with infection, and the incidence of infections is likely to be high. Therefore, the profile of infections in Japanese patients as an adverse event of particular interest (i.e., the incidence and temporal relationship with the onset of neutropenia/lymphopenia) will be determined.

c) Neutropenia

It is expected that Adcetris is used in patients with decreased neutrophil count due to prior treatment, which may increase the risk of infection and result in a high incidence of infection/severe infection. It is important to control the neutrophil count to allow for continuation of treatment (including dose reduction and restart of treatment after treatment interruption) in terms of the prevention of infection. Therefore, the profile of neutropenia in Japanese patients as an adverse event of particular interest will be determined (i.e., the status of treatment with Adcetris and neutrophil count control will be assessed and information useful for continuation of treatment with Adcetris will be collected).

d) Infusion reactions

Infusion reactions are characteristic of monoclonal antibody preparations, the profile of infusion reactions in Japanese patients as an adverse event of particular interest (including the status of premedication and the percentage of patients using premedication to prevent infusion reactions [use/non-use of premedication to prevent infusion reactions]) will be determined.

e) Pulmonary disorders

The occurrence of pulmonary disorders in Japanese patients receiving monotherapy with Adcetris as an adverse event of particular interest will be determined.

3) When to collect outcome measure data

From the start of treatment with Adcetris until the completion of 16 cycles (or upon discontinuation of treatment with Adcetris)

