Patients with a past history of malignant tumour	Patients with a past history that falls under the category of MedDRA SMQ Code 20000194 (SMQ Malignant tumours [Scope: Narrow]) (If “No concurrent illness existed at the initiation of treatment with Adcetris” is selected in the field of “Past history/concurrent illness of malignant tumours” in the case report form, the pulmonary disorder should be regarded as a past history.)
Patients with concurrent malignant tumour	Patients with a concurrent illness that falls under the category of MedDRA SMQ Code 20000194 (SMQ Malignant tumours [Scope: Narrow]) (If “A concurrent illness existed at the initiation of treatment with Adcetris” is selected in the field of “Past history/concurrent illness of malignant tumours” in the case report form, the pulmonary disorder should be as a concurrent illness.)
Patients with concurrent diabetes mellitus	Patients with a concurrent illness that falls under the category of MedDRA SMQ Code 20000041 (SMQ Hyperglycaemia/new onset diabetes mellitus [Scope: Narrow])
Patients with hypertension	Patients with a concurrent illness that falls under the category of MedDRA SMQ Code 20000147 (SMQ Hypertension [Scope: Narrow])
Patients with concurrent dyslipidaemia	Patients with a concurrent illness that falls under the category of MedDRA SMQ Code 20000026 (SMQ Dyslipidaemia [Scope: Narrow])
Patients with concurrent hyperuricaemia	Patients with a concurrent illness that falls under the category of MedDRA PT Code 10020903 (Hyperuricaemia)
Patients with concurrent infection	Patients with a concurrent illness that falls under the category of MedDRA SOC Code 10021881 (Infections and infestations)
Patients with concurrent peripheral neuropathy	Patients with a concurrent illness that falls under the category of SMQ Code 20000034 (SMQ Peripheral neuropathy [Scope: Narrow])
Patients with other concurrent illnesses	Patients with any concurrent illness other than those listed above
Antibiotics/synthetic antibacterial agents	Drugs with the first three digits of YJ Code being either one of 611 to 616, 619, or 624 that are entered in the field of “Drugs used for the prevention of infection” (If more than one antibiotics/synthetic antibacterial agents are used in the same patient, it will be counted as one patient.)
Antifungals	Drugs with the first three digits of YJ Code being 617 or the first seven

Term	Definition

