3.0 Patient Demographics and Baseline Characteristics

3.1 Patient Demographics and Baseline Characteristics

(1) Analysis sets to be used

Safety analysis set, safety analysis set (Hodgkin’s lymphoma), and safety analysis set (anaplastic large-cell lymphoma)

(2) Data to be analyzed

For each data item, patients will be stratified into the categories below, and the frequency will be calculated. In addition, summary statistics of continuous variable will be calculated:

Data item	Category
Sex	Male or female
Age	<18 years, 18 to 39 years, 40 to 64 years, 65 to 74 years, or ≥75 years
	<18 years, 18 to 64 years, 65 to 74 years, or ≥75 years
Disease duration	<1 year, <1 to 3 years, <3 to 5years, ≥5 years, or unknown
Diagnosis	Hodgkin’s or anaplastic large-cell lymphoma or other
Status	Relapsed/refractory, or new-onset
CD30	Positive, negative, or not measured
Site(s) of involvement	Lymph node, spleen, liver, lung, bone, central nerve, bone marrow, skin, and/or other
ALK (for patients with anaplastic large-cell lymphoma)	Positive, negative, or unknown
Clinical stage	I, II, III, IV, or unknown
B symptoms	Absent or present
ECOG Performance Status	0, 1, 2, 3, or 4
Therapeutic category	Outpatient, inpatient, or unknown
Hypersensitivity disposition	Absent, present, or unknown
Specific hypersensitivity disposition(s)	Medications, food allergy, and/or other
HCV antibody	Negative, positive, or unknown
HBs antigen	Negative, positive, or unknown
HBs antibody	Negative, positive, or unknown
HBV DNA	Negative, positive, or unknown
Past history of pulmonary disorders	Absent or present
Concurrent pulmonary disorders	Absent or present

Data item	Category
Past history of malignant tumours	Absent or present
Concurrent malignant tumours	Absent or present
Past history (other than pulmonary disorders and malignant tumours)	Absent, present, or unknown
Concurrent illness (other than pulmonary disorders and malignant tumours)	Absent or present
Specific concurrent illness(es) (other than pulmonary disorders and malignant tumours)	Diabetes mellitus, hypertension, dyslipidaemia, hyperuricaemia, hepatic disease(s), renal disease(s), infections, peripheral nerve disorders, and/or other
Past history (other than pulmonary disorders and malignant tumours)	Absent, present, or unknown
Concurrent hepatic disorders	Absent or present
Grade of hepatic disorder (Grade based on AST and ALT levels)	None, Grade 1, Grade 2, \geq Grade 3, or unknown
Concurrent renal disorders	Absent or present

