Patients will be stratified into the categories below and the incidence of infections considered related to Adcetris for each CTCAE grade (the worst one) will be calculated by presence or absence of drugs used for the prevention of infection, using Mann-Whitney U test. The CTCAE grade (the worst one) is higher in the order of Grades 5, 4, 3, 2, 1, and unknown. If the same patient has multiple occurrences of the same infection, the occurrence with the highest CTCAE grade will be counted once for the category.

Similar analyses will be performed by use or non-use of antibiotics/synthetic antibacterial agents or trimethoprim-sulfamethoxazole combinations and by use or non-use of trimethoprim-sulfamethoxazole combinations for bacterial infection, by use or non-use of antifungals for fungal infection, and by use or non-use of antivirals for viral infection.

For patients included in safety evaluation who use antivirals for the prevention of viral infection but experience viral infection, a list of the following items will be generated: patient number, viral infection (name of the infection), age, sex, diagnosis, past history of hematopoietic stem cell transplantation (autologous or homologous), and drugs used for the prevention of infection (antivirals). If the same patient has multiple viral infections, all these viral infections will be counted.

Data item	Category
CTCAE Grade (the worst one) of infections	None, Grade 1, Grade 2, Grade 3, Grade 4, Grade 5, or unknown

(3) Figure/table number

Tables 5.9.5-1 to 5.9.5-3 and 5.9.5-4

5.9.6 Occurrence of infections considered related to Adcetris by presence or absence of prior hematopoietic stem cell transplantation

(1) Analysis sets to be used

Patients included in safety evaluation and patients included in safety evaluation (Hodgkin’s lymphoma) or patients included in safety evaluation (anaplastic large-cell lymphoma)

(2) Data to be analyzed

The incidence of infections considered related to Adcetris for each CTCAE grade (the worst one) will be calculated by presence or absence of prior hematopoietic stem cell transplantation (absent, present [autologous], present [homologous], present [autologous and homologous], or unknown) using Kruskal-Wallis test. The grade category of “unknown” will be excluded from the test.

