5.9.13 Occurrence of adverse drug reactions of pulmonary disorder and infections

(1) Analysis sets to be used

Safety analysis set, safety analysis set (Hodgkin’s lymphoma), and safety analysis set (anaplastic large-cell lymphoma)

(2) Data to be analyzed

The incidence of pulmonary disorders considered related to Adcetris for each CTCAE grade (the worst one) will be calculated by pulmonary disorder and PT. PTs and PT Codes will be presented in ascending order.

In addition, the incidence of pulmonary disorders considered related to Adcetris for each CTCAE grade (the worst one) will be calculated by patient demographics and baseline characteristics.

The CTCAE grade (the worst one) is higher in the order of Grades 5, 4, 3, 2, 1, and unknown. If the same patient has multiple occurrences of pulmonary disorders or there are multiple occurrences of the same PT, the highest CTCAE grade (the worst one) for the patient or PT will be counted once for the category:

Data item	Category
CTCAE Grade (the worst one) for pulmonary disorders	Grade 1, Grade 2, Grade 3, Grade 4, Grade 5, or unknown

Items and categories of patient demographics and baseline characteristics

Data item	Category
History of or concurrent pulmonary disorder	Absent or present
Smoking history	Non-smoker or smoker * Patients other than those who have never smoked will be classified into “smoker.”
Prior radiotherapy	Absent or present

(3) Figure/table number

Tables 5.9.13-1 to 5.9.13-4

5.10 analysis setanalysis setanalysis setList of actions taken with Adcetris in patients experiencing peripheral nerve disorders considered related to Adcetris

(1) Analysis sets to be used

Patients included in the safety analysis set analysis setanalysis setwho experience peripheral nerve disorders considered related to Adcetris

(2) Data to be analyzed

(3) For each patient, a list of the following data items: patient number, diagnosis, action taken or not taken with Adcetris, reason for action taken, date of dosing and dose for each cycle, date of onset of peripheral nerve disorder, CTCAE grade (the worst one), outcome, and the date of outcome. If the

same patient has multiple occurrences of peripheral nerve disorder, all these occurrences will be counted. Figure/table number

Table 5.10

5.11 List of actions taken with Adcetris in patients experiencing neutropenia considered related to Adcetris

(1) Analysis sets to be used

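### Baseline infection is recorded and coded but enters no infection analysis, so the prophylaxis comparison in SAP 5.9.5 is open to confounding by indication

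*Protocol*

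**What the plan says.** Protocol 9.2.5 2) b) explains why infections are an event of particular interest. It expects Adcetris to be used in immunocompromised patients or, as the alternative, in "those who are complicated with infection, and the incidence of infections is likely to be high". The enrolment form (Protocol 9.1) collects "presence/absence of infections, peripheral nerve disorders, hepatic disorders, severe renal disorders", and concurrent illnesses are also recorded on the case report form (Protocol 9.2.2).

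The definitions table in Section 1 of the current SAP derives the flag for concurrent infection: "Patients with a concurrent illness that falls under the category of MedDRA SOC Code 10021881 (Infections and infestations"). It is used twice. SAP 3.1 counts it among specific concurrent illnesses ("hepatic disease(s), renal disease(s), infections, peripheral nerve disorders, and/or other"), and SAP 4.3 tabulates it by initial dose.

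Infections considered related to Adcetris are compared in two tested analyses. In SAP 5.9.5 the incidence by worst CTCAE grade is "calculated by presence or absence of drugs used for the prevention of infection, using Mann-Whitney U test", with similar analyses for bacterial, fungal and viral infections against the matching drug classes. SAP 5.9.6 compares groups by prior stem cell transplantation with a Kruskal-Wallis test. Neither is split by concurrent infection.

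**The concern.** Four of the five events of particular interest have an obvious baseline counterpart. Three of them are tabulated by it: peripheral nerve disorders by concurrent peripheral nerve disorder (SAP 5.9.2), neutropenia by baseline neutrophil grade (5.9.7) and pulmonary disorders by "History of or concurrent pulmonary disorder" (5.9.13). Infection is the exception, although the protocol itself points to patients who start with one.

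The consequence falls mainly on 5.9.5, which carries a test at the SAP's two-sided 5% level. If patients infected at the start are both more likely to be given preventive drugs and more likely to have a later infection, the crude comparison mixes that indication with any effect of the drugs. A reader could then take prophylaxis to be useless or harmful. The surveillance would also give no infection incidence for patients who begin treatment free of infection.

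**Working it through.** **The plan's own figure.** The only design calculation is the enrolment of 140, set to see at least 10 infusion reactions with 95% probability at a rate of 11%. The exact binomial gives P(X ≥ 10 | n = 140, p = 0.11) = 0.952, and 140 is the smallest n that reaches 0.95. The figure reproduces. This point does not depend on it, except that 140 is used below as the planned size.

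**Where the flag is used.**

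| Analysis | Split by baseline infection? |
|---|---|
| SAP 3.1, 4.3 | Shown, but not against an infection outcome |
| SAP 5.1.2 (reactions by SOC and PT) | No |
| SAP 5.3 (any adverse drug reaction, by factor) | No; concurrent pulmonary, malignant, hepatic and renal disorders are listed |
| SAP 5.4 to 5.6 (age, hepatic, renal) | No |
| SAP 5.9.5, 5.9.6 | No |
| Supplemental SAP 2.2.1, 2.2.2 (infections after Grade 3 or 4 neutropenia or lymphopenia) | No |

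**Illustration of size.** The documents give neither the prevalence of baseline infection nor prophylaxis use by that status, so every input here is an assumption. Let s be the share infected at baseline. Prophylaxis is used in 90% of infected and 60% of other patients. Later related infection occurs in 50% and 25%, and prophylaxis has no effect.

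- Infected share among prophylaxis users: w1 = 0.9s / [0.9s + 0.6(1 − s)]
- Infected share among non-users: w0 = 0.1s / [0.1s + 0.4(1 − s)]
- Crude risk in each group: 0.50w + 0.25(1 − w)

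| s | w1 | w0 | Users | Non-users | Difference | Ratio |
|---|---|---|---|---|---|---|
| 0.10 | 0.09/0.63 = 0.143 | 0.01/0.37 = 0.027 | 28.6% | 25.7% | 2.9 points | 1.11 |
| 0.20 | 0.18/0.66 = 0.273 | 0.02/0.34 = 0.059 | 31.8% | 26.5% | 5.3 points | 1.20 |

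Among patients without baseline infection both groups have 25%, so the false difference disappears there. It is also zero overall if baseline infection does not change later risk, or if prophylaxis use is the same with and without it.

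**Sensitivity.** Take an overall incidence of 61% (Protocol 3.2: infections in the pooled non-Japanese phase 2 studies). Let 5% to 30% be infected at baseline, with a risk ratio of 1.25 to 1.5 and prophylaxis use of 90% versus 60% or 95% versus 50%. The false excess then runs from 0.9 to 10.8 points. With an assumed overall incidence of 30% and risk ratios of 1.5 to 3, it runs from 0.9 to 15.3 points.

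**Against sampling error.** With 140 patients and the first set of inputs, users and non-users number 88.2 and 51.8 (s = 0.10) or 92.4 and 47.6 (s = 0.20). The standard error of the difference is 7.7 or 8.0 points, a 95% half-width of about 15 to 16 points. In a two-proportion approximation, false rejection rises from 5% to about 7% and 10%.

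**Stratum sizes.** Infected at baseline: 140 × 0.10 = 14 to 140 × 0.20 = 28. Infected and without prophylaxis: 14 × 0.1 = 1.4 to 28 × 0.1 = 2.8. Not infected at baseline: 126 to 112.

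**The case against.** **The infection aim is met as stated.** Protocol 9.2.5 2) b) asks for incidence and for timing relative to neutropenia and lymphopenia. SAP 5.1.2 and the first supplement supply these. Risk factors are promised for neuropathy, not for infection, and no prophylaxis effect is promised. This stands, and it limits the weight of the point. But the SAP chose to add a tested prophylaxis comparison, and that comparison should be readable.

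**The link to prophylaxis is assumed.** The case report form field asks for preventive drugs, not treatment of an existing infection. The outcome counts only infections not judged unrelated, which should remove some that merely continue from baseline. Both may weaken the associations. Neither balances the groups, and only the missing table would show what remains.

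**The bias may be small beside the noise.** On the first set of inputs this is right. It argues against a stratified test such as van Elteren: with perhaps 1 to 3 infected patients off prophylaxis, that stratum adds almost nothing. It does not argue against showing the split.

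**Stronger readings that a reader might infer, and that the documents do not support:**

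- That the protocol expects infections mainly in patients already infected. The clause, short of its last word, is "immunocompromised due to prior treatment or the prior disease or those who are complicated with infection, and the incidence of infections is likely to be". The immunocompromised come first and neither group is ranked.
- That the comparisons are shown to be confounded. They are open to it; the documents hold no data either way.
- That infections are examined only by prophylaxis and transplant. They also appear in 5.1.2, 5.4 to 5.6 and the first supplement.
- That 5.9.6 needs adjustment. Prior transplantation precedes infection status at the start of Adcetris, so baseline infection may lie on the pathway to later infection. Adjusting could remove part of the association of interest.

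**Conclusion.** The omission is a fact of the documents. Baseline infection is named in the rationale, collected and coded, yet no infection analysis in the current SAP or its supplements uses it, unlike the three comparable events. The result is that 5.9.5 is open to confounding by indication and that infection incidence in patients starting free of infection goes unreported.

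The size is unknown. The excess of 2.9 to 5.3 points rests wholly on the assumed prevalence, risks and prophylaxis use; other assumptions give 0.9 to 15.3 points, and none if either association is absent. The point is a modest one in a largely descriptive surveillance, but it bears on a tested comparison and is nearly free to address.

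**What to change.** In SAP 5.9.5:

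- Tabulate related infections by worst grade separately for concurrent infection absent and present at baseline, using the SAP's existing definition.
- Repeat the existing Mann-Whitney test in patients without concurrent infection, beside the crude result. The same restriction can serve the bacterial, fungal and viral comparisons, because a patient with no coded infection is free of each type.
- State that the comparison is descriptive and does not estimate a prophylaxis effect.

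In SAP 5.9.6, add the same split as description only, without adjustment. A concurrent-infection row in 5.3 is optional: that section counts any adverse drug reaction, so it would not answer the infection question.

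The cost is SAP wording and a few table rows, with no new data or definition. The infected stratum will probably be small and its percentages imprecise.

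The split leaves a separate problem untouched. Preventive drugs are recorded over the whole observation period (Protocol 9.2.3), and 5.9.5 does not require them to have started before the infection. That is a further reason to label the comparison descriptive.
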